6.4 STUDY INTERVENTION COMPLIANCE

In order to evaluate the efficacy, safety and tolerability of the study device, it is critical that subjects use the study device as directed. All unused devices will be disposed of. Only one device is to be used at a time. All study devices are to be self-administered by the study subject or a trained caregiver. Subjects will be required to answer a question using the daily stool diary regarding administration of their study devices each day during the treatment period.

If a subject does not receive or use all assigned study devices, the reason is to be recorded in source documents and the CRF.

Subject will be contacted via telephone by the study site personnel during the study to encourage the subject to be compliant in completion of daily bowel diaries and questionnaires and to ensure reporting of adverse events.

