6.7 PARTICIPANT DISCONTINUATION/WITHDRAWAL FROM THE STUDY

If signs of a major side effect (e.g., rectal perforation) should occur, the subject will be treated as clinically indicated and Principal Investigator and Sponsor will be notified immediately. Such events will be reported on the case report form.

Patients with AEs will be evaluated by the investigator. An anoscopy will be performed to determine the etiology of anal pain or bleeding and if a significant anal-rectal abnormality is identified the patient will exit the study. Any data collected from a patient who is withdrawn because of an AE will be included in the ITT safety but not effectiveness summary. Any patient with a mucosal abnormality should be followed to resolution. After the treatment period, all individuals who withdraw for reasons other than personal preference (i.e., for medical reasons) and a minimum of 50% of all patients shall undergo an evaluation by anoscopy following the treatment period to assess for device related trauma.

Subjects will be informed that they have the right to withdraw from the study at any time for any reason, without prejudice to their medical care, penalty or loss of benefits. If the subject withdraws, they should be treated with standard of care. The Investigator also has the right to withdraw subjects from the study for any of the following reasons:

- Adverse events which, in the judgment of the Investigator, justify treatment study withdrawal
- Non-adherence to study device use regimen or protocol requirements
- Non-compliance with instructions
- General or specific changes in the subject's condition unacceptable for further treatment in the judgment of the Investigator
- Subject requires use of an unacceptable concomitant medication
- Subject no longer meets the protocol criteria (Section 4.2)
- Subject request
- Administrative reasons

If a subject is withdrawn or discontinued from the study, the primary reason for withdrawal from the study is to be recorded in the source documents and the Case Report Form. All subjects withdrawn prior to completing the study should be encouraged to complete study safety assessments.

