7.2 SAFETY AND OTHER ASSESSMENTS

The following procedures/evaluations will be performed for safety assessments:

- **Screening visit** – Review of medical history, physical examination (including rectal examination) following consent, vital signs [ie, temperature, pulse, and blood pressure], height and weight
- **Assess adherence to intervention. Inquire about adverse events with phone calls during the fitting and treatment periods.**
- **Review medical records** prior to and during study participation for adverse events. This process will adhere to Health Insurance Portability and Accountability Act (HIPAA) rules, other relevant federal or state laws, and local institutional requirements should be followed, as applicable.
- **Administer questionnaires and a daily diary to record subject-reported outcomes**
- **Assessment of adverse events.** Adverse events will be evaluated promptly. Subjects will be referred for additional tests and/or provided treatment.

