8.3 POPULATIONS FOR ANALYSES

Male and female, aged 18 and above, with a diagnosis of fecal incontinence. For the main and the sub-study, the analyses will follow the intent to treat (ITT) paradigm with all subjects randomized included in the analyses. Subjects with missing values for a particular endpoint will have their missing values imputed using the corresponding overall mean value from all subjects with non-missing data for that endpoint. An adjustment in the ANCOVA error degrees of freedom (subtracting one for each imputed value) will be made to account for the imputation. A similar adjustment for the Wilcoxon rank sum test (adjusting the degrees of freedom for the t-approximation) will also be examined. Similar analyses will be performed for the completer cohorts, i.e., all subjects who completed the 4 week treatment bowel diary and the [REDACTED] sub-study. For the bowel diary study, the modified ITT (mITT) cohort, which comprises those subjects who entered treatment and completed at least 1 week of device use will also be considered.

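### Section 6.7 leaves adverse-event withdrawals out of effectiveness although 8.3 promises ITT, and 8.3 fills missing endpoints with the mean of subjects who have data

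*Combined protocol and SAP*

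**What the plan says.** On AE withdrawals, section 6.7 is explicit. After anoscopy for pain or bleeding, "if a significant anal-rectal abnormality is identified the patient will exit the study". It then adds: "Any data collected from a patient who is withdrawn because of an AE will be included in the ITT safety but not effectiveness summary".

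Section 8.3 says that "the analyses will follow the intent to treat (ITT) paradigm with all subjects randomized included in the analyses". The main study randomises nobody (section 6.3 describes a within-subject control; randomisation appears only in the exploratory procedures of 7.1), so the set is not literally defined. Section 8.3 also says that subjects lacking a value will have "missing values imputed using the corresponding overall mean value from all subjects with non-missing data for that endpoint", with one error degree of freedom removed per imputed value. It adds completer and mITT analyses; mITT requires a week or more on the device.

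On other withdrawals, sections 5.4 and 6.7 give the investigator the right to withdraw a subject for "Non-adherence to study device use regimen or protocol requirements". On follow-up, both say: "All subjects withdrawn prior to completing the study should be encouraged to complete study safety assessments". Section 7.2 includes this item in its list of safety procedures: "Administer questionnaires and a daily diary to record subject-reported outcomes". Section 6.4 has subjects answer a diary question "regarding administration of their study devices each day during the treatment period".

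The Schedule of Activities (1.3) collects FISS and FI QOL twice: at the end of baseline and at the end of treatment.

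**The concern.** Subjects withdrawn because of an AE are those the device may have hurt or who could not tolerate it. An ITT effectiveness analysis should count them. Section 6.7 removes even the data they have already given, and 8.3 would replace a missing value with the average result of everyone else. Either way, a result labelled ITT describes people who stayed on the device.

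The supporting analyses do not repair this. Completers exclude withdrawn subjects by definition, and mITT carries no rule for them that would. The degrees-of-freedom adjustment concerns precision and leaves the mean where it is.

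What is at stake is the reported size of the effect. Section 3 justifies the primary endpoint by substantial equivalence to a predicate device. Section 9.1.6 names that predicate, and sections 2.1, 2.2 and 4.2 report that 62% of its subjects had at least a 50% reduction, on an intent-to-treat basis. Readers will set this trial's rate beside that figure, although no test of that comparison is planned.

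**Working it through.** **The plan's own figures.** Section 8.2 uses a two-sided paired t test, alpha 0.05, difference 1.3 and SD 1.3. Exact power is 88.3% with 12 subjects and 91.1% with 13, so the stated 13 is reproduced. For the binomial test of 30% against 60% with n = 30, rejecting at 15 or more responders has an upper tail of 0.0169 and power of 90.3%, matching the stated 90%. The sample size is not in dispute.

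**Inputs.**
- From the documents: 60 treated subjects (4.1); 2.6 episodes/week at baseline and 1.3 on the device (8.2); a 28-day treatment period; 70% of subjects reaching a 50% reduction (8.4.1), used here for continuing users.
- Assumed: immediate return to 2.6 when use stops; k = 3 or 6 AE withdrawals during treatment; no withdrawn subject responds. No dropout rate is planned for this trial. For earlier anal plugs, sections 2.1, 2.2 and 4.2 cite 12.5% to 68%.

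**1. True 28-day reduction if use stops after day t.**
r = 1 − [(t/7) × 1.3 + ((28 − t)/7) × 2.6] / 10.4
- Day 7: 1 − 9.1/10.4 = 12.5%
- Day 14: 1 − 7.8/10.4 = 25.0%
- Day 21: 1 − 6.5/10.4 = 37.5%

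**2. Reported mean.** Dropped: the mean of the remaining 60 − k subjects is 50%. Mean-filled: [(60 − k) × 50 + k × 50]/60 = 50%. These are identical, so for the unadjusted mean it does not matter which the sponsor does.

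**3. Overstatement of the mean reduction** = (k/60) × (50 − r).

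| k | stop day 21 | stop day 14 | stop day 7 |
|---|---|---|---|
| 3 | 0.6 | 1.25 | 1.9 |
| 6 | 1.3 | 2.5 | 3.8 |

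**4. Responder rate.** True rate = 0.70 × (60 − k)/60, which is 66.5% (k = 3) or 63.0% (k = 6). Reported rate: 70% if subjects are dropped or the binary endpoint is mean-filled. If a 50% reduction is imputed first and then dichotomised at 50%, every filled subject becomes a responder: (0.70 × 57 + 3)/60 = 71.5% and (0.70 × 54 + 6)/60 = 73.0%.

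**5. FISS and FI QOL.** The post-baseline value of an early withdrawal is wholly missing, so the fill applies in full. If withdrawn subjects have no change, the mean change is inflated by 60/(60 − k) − 1, which is 5.3% (k = 3) or 11.1% (k = 6).

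**6. The test against 30%.** With an upper tail of 0.025, 26 of 60 is enough (tail 0.0196). The true rates in step 4 correspond to about 40 and 38 responders of 60, so the conclusion is the same with or without the overstatement.

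**The case against.** The strongest reply concerns subjects who simply stop using the device. A reader might infer that such subjects are removed and then followed for safety alone. The documents do not support that. Withdrawal for non-adherence is a right of the investigator, not a duty, and its effect is zero if stoppers are kept. The plan expects some non-use: 6.4 asks about it daily and requires reasons, and 8.4.2 averages the diary over four weeks with no readable rule that drops off-device days. That follow-up is for safety alone is a reading of silence, because 7.2 counts the diary and questionnaires among the safety procedures. The text introducing the methods in 8.4.2 is redacted, and no rule for a partial diary can be read. For non-adherence withdrawals, the effect on the diary endpoint is therefore unknown. All of this stands.

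It does not reach the AE sentence, which is readable and excludes collected data outright. A sponsor might answer that 8.3 overrides 6.7. Recorded diary days would then count in some unknown way, but FISS and FI QOL would still be mean-filled for early withdrawals.

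Two further replies have some force. The replacement rule is partly a choice of estimand; but 8.3 has already chosen ITT, and the observed mean does not serve it when those who leave do worse. Also, the assumption that no withdrawn subject responds is not general: someone stopping after day 21 with a 66.7% on-device reduction still reaches 66.7 × 21/28 = 50% over the period.

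**Conclusion.** The point holds for AE withdrawals. Sections 6.7 and 8.3 contradict each other, and following either the exclusion or the mean fill overstates effectiveness whenever withdrawn subjects do worse than those who continue. With 3 or 6 such withdrawals in 60, the overstatement is 0.6 to 1.9 or 1.3 to 3.8 points of mean reduction. On the responder scale it is 3.5 or 7.0 points (5.0 or 10.0 if imputed before dichotomising). With 6 withdrawals, a true rate 1 point above the predicate's 62% would be reported as at least 8 points above it. These figures illustrate stated assumptions and do not forecast the trial. For non-adherence withdrawals the concern is the same in kind, but its size may be zero and cannot be fixed from the readable text.

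A reader might infer that the trial could declare success falsely. The scenarios here do not show that. On the same assumptions it would take about 24 withdrawals of 60, leaving 0.70 × 36 ≈ 25 responders, to fall short of 26. That 40% lies inside the range cited for earlier plugs, but the range comes from other devices and is not specific to AEs. The 70% in 8.4.1 is an expectation with no test attached. The plan should still be changed, because the reported effect size is what will be compared and quoted.

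**What to change.** 1. **Section 6.7.** Change the AE sentence so that data collected from AE withdrawals enter the ITT effectiveness analysis as well as the safety summary.
2. **Section 8.3.** Define the ITT set as all subjects who enter the treatment period. Do not impute the observed mean for subjects who stop the device or withdraw. Count them as non-responders when a responder endpoint is missing. Fill missing diary days after stopping with the subject's own baseline daily rate, and use the baseline value for FISS and FI QOL. Keep the completer analysis for on-device results. Report how many stopped and why, including losses during fitting, who fall outside this set.
3. **Sections 5.4 and 6.7.** Ask subjects who stop the device during the treatment period, but do not withdraw consent, to keep the mailed diary to treatment day 28 and complete the end-of-treatment questionnaires. For this, an abnormality found at anoscopy should end device use without automatically ending diary collection. The clinical rules for stopping the device stay as they are.

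The cost is wording in three sections, some diary burden, longer contact and AE follow-up after stopping, and possibly a lower effect estimate. Subjects who withdraw consent give no further data and are covered only by the rule in item 2.

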6.8 LOST TO FOLLOW-UP

A subject will be considered lost to follow-up if he or she is unable to be contacted by the study site staff.

The following actions must be taken if a subject fails to return to the clinic for a required study visit:

- The site will attempt to contact the subject and reschedule the missed visit and counsel the subject on the importance of maintaining the assigned visit schedule and ascertain if the subject wishes to and/or should continue in the study.
- Before a subject is deemed lost to follow-up, the investigator or designee will make every effort to regain contact with the subject (where possible, 3 telephone calls, electronic emails or texts and, if necessary, a certified letter to the subject's last known mailing address or local equivalent methods). These contact attempts should be documented in the subject's medical record or study file.
- Should the subject continue to be unreachable, he or she will be considered to have withdrawn from the study with a primary reason of lost to follow-up.]

7 STUDY ASSESSMENTS AND PROCEDURES

7.1 SAFETY AND EFFICACY ASSESSMENTS

Inclusion Criteria Assessment

An assessment of accidental bowel leakage and the ability to retain the device is performed as part of subject screening. This assessment includes a questionnaire which asks subjects about bowel leakage frequency and intensity.

Daily Bowel Diary Assessment

Subjects will complete a daily bowel diary card on which each subject will be asked to record every bowel event. The card includes a questionnaire onto which subjects will record details relating to bowel event cause, stool type, leakage, pain, urgency, medications used, and study device usage.

Weekly Global Fecal Incontinence Assessment

Subjects will complete a weekly questionnaire to assess global fecal incontinence. The questionnaire records subject overall relief of incontinence symptoms each week.

Fecal Incontinence Severity (FISS) Assessment

Subjects will complete a questionnaire to assess fecal incontinence severity (FISS) at the end of the baseline period and at the end of the treatment period. The questionnaire records the severity of subject fecal incontinence.

Fecal Incontinence Quality of Life (FI QOL) Assessment

Subjects will complete a questionnaire to assess fecal incontinence quality of life (FI QOL) at the end of the baseline period and at the end of the treatment period. The questionnaire records the subject quality of life in relation to fecal incontinence.

Patient Reported Outcomes Measurement Information System (PROMIS) Anxiety Assessment

Subjects will complete a questionnaire to assess their level of anxiety using the PROMIS short form instrument Emotional Distress – Anxiety 8a.

Patient Reported Outcomes Measurement Information System (PROMIS) Depression Assessment

Subjects will complete a questionnaire to assess their level of depression using the PROMIS short form instrument Emotional Distress – Depression 8a.

Credibility/Expectancy Assessment

Subjects will complete a questionnaire to assess their level of belief that the therapy received will reduce their anxiety relating to fecal incontinence. The questionnaire gathers information relating to what each subject thinks will happen during treatment, and what each subject feels will happen during treatment.

User Satisfaction Assessment

Subjects will complete a Quebec User Evaluation of Satisfaction with assistive Technology (QUEST) questionnaire to assess their level of satisfaction with the study device. The questionnaire gathers information relating to user satisfaction with various aspects of the device and service provided during treatment.

Exploratory Study Assessments: [REDACTED] Procedures (for [REDACTED] sub-study subjects only)

A schema and rationale for the [REDACTED] is as follows.

Table 1. Schedule of Events – [REDACTED].

Steps	Purpose
i) [REDACTED] will be performed if this not been performed previously*	i) Evaluate for [REDACTED]
- ii) [REDACTED] and randomize subjects, equally [REDACTED] to one	ii) Evaluate device [REDACTED]

of [REDACTED] groups: [REDACTED] Minnesota Medical Technologies Anal Insert Device (10 mm), and Minnesota Medical Technologies Anal Insert Device (13 mm). [REDACTED]. Measure [REDACTED]. Remove subjects [REDACTED]. Then [REDACTED]. Ask subjects and measure [REDACTED]. Compare [REDACTED].
 
iii) Add [REDACTED] (until [REDACTED]) to [REDACTED].
 
iv) [REDACTED] subject [REDACTED] randomize subjects to 10 mm or 13 mm device. Obtain [REDACTED]
	
iii) Determine [REDACTED]
 
iv) Assess a) relationship between [REDACTED] b) rectoanal [REDACTED] and c) ability to [REDACTED].

--	---

*With one exception, ie, the use of the Minnesota Medical Technologies Anal Insert Device, [REDACTED] is comparable to that performed in clinical practice.

** [REDACTED]: The [REDACTED] consists of the [REDACTED] the Minnesota Medical Technologies Anal Insert Device [REDACTED]. The [REDACTED] prepared by [REDACTED] the device. A [REDACTED], approximately [REDACTED], is passed through [REDACTED]. The [REDACTED] is placed [REDACTED] and [REDACTED] with the [REDACTED].

Randomization to 10 or 13 mm device

This [REDACTED] include these assessments arranged in chronological order. We anticipate that these studies will be performed in [REDACTED]. Established techniques used in our clinical practice and research will be used [REDACTED]

[REDACTED]

After [REDACTED], the anal [REDACTED]

[REDACTED] in conjunction with a [REDACTED]

[REDACTED] will be categorized [REDACTED]

[REDACTED]).

(ii) [REDACTED] test

[REDACTED] randomize subjects, equally (i.e., [REDACTED] each) to one of [REDACTED] groups: [REDACTED] Minnesota Medical Technologies Anal Insert device (10 mm), and Minnesota Medical Technologies Anal Insert device (13 mm). In the [REDACTED] group, [REDACTED], in [REDACTED] [REDACTED] device. Then, apply [REDACTED]. Measure [REDACTED]. Then, [REDACTED]. Ask subjects [REDACTED] as follows: [REDACTED], [REDACTED], and [REDACTED]. Now [REDACTED] and measure [REDACTED]. Remove subject [REDACTED], [REDACTED], and [REDACTED]. [REDACTED] after reporting [REDACTED].

(iii) Anal [REDACTED] rectum

[REDACTED] rectum and [REDACTED]. The [REDACTED]. Thereafter, subjects should be [REDACTED]. [REDACTED] [REDACTED] the device in situ]. A [REDACTED] will be documented by measuring [REDACTED]

(iv) Evaluate [REDACTED] the device

Subjects should [REDACTED]. Add the anal insert device, randomizing subjects to 10mm or 13mm device. Then [REDACTED]

[REDACTED]. [REDACTED] will be measured with a [REDACTED]

[REDACTED]

(v) Subjects will be asked to [REDACTED]

If the insert device was [REDACTED], document if the device is [REDACTED]. If it was [REDACTED], ask subjects to [REDACTED].

Assessment: [REDACTED]

This will be performed in all subjects at baseline unless this had been performed within 6 months prior to consent. [REDACTED] will be performed using established validated approaches that our used in our clinical practice and research studies. After [REDACTED]

Protocol Number IRB-18-004642

with [REDACTED] will be assessed using standard and established techniques in [REDACTED] will be measured [REDACTED] by [REDACTED] [REDACTED]. Since clinical observations suggest that [REDACTED] [REDACTED], [REDACTED] will also be assessed.

Anoscopy will also be performed for subjects who complain of new anorectal bleeding or moderate or severe pain on the bowel diary. After the treatment period, all individuals who withdraw for reasons other than personal preference (i.e., for medical reasons) and a minimum of 50% of all patients shall undergo an evaluation by anoscopy following the treatment period to assess for device related trauma

Assessment: [REDACTED]

This test will be done in all subjects either just prior to [REDACTED] or during the initial visit in subjects who [REDACTED]. Similar to ongoing studies in [REDACTED], we propose to use [REDACTED], which is a [REDACTED] comprised of [REDACTED] [REDACTED] is used to [REDACTED]. It is FDA cleared (FDA K [REDACTED]) for [REDACTED] with an [REDACTED] The [REDACTED] [REDACTED] and the [REDACTED]. The [REDACTED] of the [REDACTED] when [REDACTED] and the [REDACTED]. We propose to [REDACTED] under [REDACTED] during the rectal examination. Once the [REDACTED], the [REDACTED] will be [REDACTED] into the rectum and the [REDACTED]. This will [REDACTED] [REDACTED]. The [REDACTED] will be [REDACTED] in the [REDACTED] with the [REDACTED]. The [REDACTED] then be [REDACTED].

Assessment: [REDACTED]

1. [REDACTED] to [REDACTED] [REDACTED] will be used as described in literature [REDACTED]. The [REDACTED] will be calculated by [REDACTED] with subject [REDACTED] and a [REDACTED] to assess [REDACTED].
2. [REDACTED] analysis: [REDACTED] will be using standardized methods [REDACTED]. [REDACTED] of the [REDACTED] will be [REDACTED] which has been validated for use [REDACTED]. With the [REDACTED] will include both the [REDACTED] analysis [REDACTED]. [REDACTED] of the [REDACTED] will be [REDACTED] using [REDACTED] has been validated for standard use by [REDACTED]. The [REDACTED] will

ensure [REDACTED]. [REDACTED] will yield [REDACTED] () and [REDACTED] [REDACTED] data. In order to accomplish this task we will follow protocols that we have quantitatively shown to be optimal.

[REDACTED] using our [REDACTED] () that has been [REDACTED]

[REDACTED] . [REDACTED] will be [REDACTED]

[REDACTED] be used to [REDACTED] that will be used in [REDACTED]

Second,

[REDACTED] following published protocols [REDACTED]. Similarly, [REDACTED] will be [REDACTED]

[REDACTED] . The [REDACTED] will be [REDACTED]

[REDACTED] . Subsequent [REDACTED] may also be performed.

3. Assessment: [REDACTED] will be assessed at baseline using a [REDACTED] ().

This questionnaire is based on the [REDACTED] and has been adapted by [REDACTED] in an electronic computer-administered format to evaluate [REDACTED] over a three month period. It employs the [REDACTED] database for [REDACTED]. The [REDACTED] been validated and compares well with [REDACTED].

[REDACTED] (ii) Subjects will [REDACTED] prior to [REDACTED] analysis. The [REDACTED] will be analyzed for [REDACTED] staff using the [REDACTED] developed by [REDACTED].

4. [REDACTED] analysis. Mayo Clinical is currently exploring [REDACTED]

[REDACTED] Towards our long-term objective of [REDACTED] study subjects. The [REDACTED] will be [REDACTED]

[REDACTED] . The [REDACTED] will be [REDACTED] . [REDACTED] will be conducted [REDACTED] or comparable approaches. All subjects who qualify for the study based on physician assessment in Period 1 [REDACTED] . [REDACTED] will be examined using these subjects and [REDACTED].

5. Analysis of [REDACTED] . In order to investigate [REDACTED], we will [REDACTED] at Mayo Clinic Rochester. We will [REDACTED] at the time of the initial visit. [REDACTED] Further [REDACTED] will be [REDACTED] at Mayo Clinic, Rochester.

Summary of [REDACTED]. The [REDACTED] for this study [REDACTED].

Item	Test ID	Lab	[REDACTED])
[REDACTED] and	[REDACTED]	[REDACTED]	Use [REDACTED])
			[REDACTED])

